#### **8.4. Study Power and Accrual Target**

This study has been designed to provide 83% power to detect a 50% risk reduction in the hazard rate for progression to Stage 2 or 3 T1D (abnormal glucose tolerance or diabetes diagnosis) using a two-sided test at the 0.05 level after a minimum of two years of follow-up on all participants and an expected total study duration (accrual and follow-up) of six years. We note that if accrual is more rapid than expected, minimum follow-up on participants may need to be extended in order to meet the number of events required for the final analysis.

A total of 201 participants will be randomized in a 2:1 allocation to treatment with hydroxychloroquine (n=135) vs. placebo (n=66). Randomization will be conducted using block randomization with variable block sizes with stratification on (1) whether or not participants have been previously treated for T1D prevention, and (2) age group (< 8 years old vs. 8 years old or older).

The assumptions underlying the estimated sample size for this design are: (1) 40% two-year event rate in the placebo group, (2) detectable hazard ratio of 0.50 (i.e. 22.5% two-year event rate) in the hydroxychloroquine group, (3) less than a 10% two-year dropout rate in both groups, and (4) survival curves which are consistent with exponential survival distributions. Even testing for variable proportions of each stratum and with slight variation in the expected hazard rates for the placebo group across the strata, our proposed sample size of 201 participants will provide at least 83% power to detect a hazard ratio of 0.50 in the time to T1D stage progression between the two treatment groups using a stratified Cox regression model.

Under the above assumptions, the target total number of events is equal to 80; i.e., the final analysis will be conducted once 80 events (confirmed abnormal glucose tolerance, diabetes) have been observed. If the accrual rate is 50 patients per year, with the above assumptions it is estimated that the enrollment period will last approximately 4 years with a total study duration of approximately 6 years (4 years of accrual + minimum of 2 years of follow-up) to provide a sufficient number of events to detect the assumed difference.

The final test of significance up to the six-year time point will employ group sequential critical values to protect against inflation in the type I error probability due to interim assessments of the emerging data for review by the DSMB (see Section 8.5).

Note the accrual period and the study sample are only projections, since the actual accrual rate and the loss-to-follow-up rate are unknown. As the study progresses, more accurate projections of the study end date will be computed based on the observed rate of enrollment, the observed number of events, and the observed rate of loss-to-follow-up. These data will be provided to the DSMB and the TrialNet governing body, and if need be, this document will be amended.

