### **3.9. Study Timeline**

#### **3.9.1. Study Duration**

The study has been designed to provide 83% power to detect a 50% risk reduction in the progression from Stage 1 to Stage 2 or 3 T1D using a two-sided test at the 0.05 level after six years of study duration (approximately 4 years of accrual and a minimum of 2 years of follow-up on all subjects). A total of approximately 201 participants will be allocated in a 2:1 ratio to the two groups.

The assumptions underlying the sample size are: 1) 40% two-year event rate in the placebo group for the progression from Stage 1 to Stage 2 or 3 T1D, 2) detectable hazard ratio of 0.50 (i.e., reducing the hazard rate by 50%, which here translates to 40% vs. 22.5% in the two-year event rates) in the hydroxychloroquine group, 3) a 10% or less dropout rate for a minimum of 2 years of follow-up on all participants in both groups, and 4) assumption that the distribution of time to T1D stage progression is approximately exponentially distributed. Under the above assumptions, the total target number of events that would trigger the final analysis is 80; i.e., the final analysis will be conducted once 80 events (abnormal glucose tolerance or diabetes) have been observed. If the accrual rate is 50 patients per year, with the above assumptions it is estimated that the enrollment period will last approximately 4 years, with a total study duration of approximately 6 years to provide a sufficient number of events to detect the powered detectable difference.

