1. Evidence that the HR is not constant over the period of follow up will be assessed and the risk of diabetes will be assessed in a PH model. The primary test for treatment effect is based on the Cox model, which assumes a proportional hazard between treatment groups. If there is a true treatment effect but it is not proportional over the follow-up period the test will have substantially less statistical power than stated in the statistical section of the protocol. Therefore, to establish a reasonable guide to pursue the possibility of a non-proportional treatment effect we will use the guideline requiring a significance level of 0.10 or less of the LRT from the standard Cox model. Graphical diagnostics using Schoenfeld residuals will be employed to explore evidence for a monotonically decreasing effect of treatment over the follow-up period. Also, plotting the Kaplan-Meier time-to-AGT rates by treatment group on the log-log scale will provide visual assessment of any diminishing effect of treatment (equal distance separation of curves indicates proportional hazard). We will characterize any such decreasing effect of treatment by model parameterization with monotonically decreasing benefit over the follow-up time. Initially, a treatment interaction with log-transformed time-on-study will be fit to the data and the log likelihood improvement in the fit noted. Other time transforms will be explored only to characterize mathematically the rate of the diminishing effect. Of particular interest will be characterizing the point in follow-up where the hazard ratio is 1. Any variations in proportional hazards other than a monotonically decreasing effect will not be of interest because of the possibility that it is simply random error.

5. Study Power and Sample Size

This study has been designed to provide 83% power to detect a 50% risk reduction in the hazard rate for progression to Stage 2 or 3 T1D (abnormal glucose tolerance or diabetes diagnosis) using a two-sided test at the 0.05 level after a minimum of two years of follow-up on all participants and an expected total study duration (accrual and follow-up) of six years. We note that if accrual is more rapid than expected, minimum follow-up on participants may need to be extended in order to meet the number of events required for the final analysis.

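### Two end-of-trial conditions, 80 events and two years of follow-up on everyone, do not coincide under the plan's own inputs, and no precedence is given

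*Protocol*

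**What the plan says.** Protocol 8.4 sets an event trigger: "the final analysis will be conducted once 80 events (confirmed abnormal glucose tolerance, diabetes) have been observed". Section 3.9.1 and SAP section 5 carry the same 80-event rule.

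The same sections state a follow-up condition. Protocol 8.4 places the 83% power "after a minimum of two years of follow-up on all participants and an expected total study duration (accrual and follow-up) of six years"; 3.9.1 describes "approximately 4 years of accrual and a minimum of 2 years of follow-up on all subjects"; SAP section 5 repeats "after a minimum of two years of follow-up on all participants".

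The only adjustment described, in both documents, is to lengthen minimum follow-up if accrual is faster than expected. Both also call the accrual period and study sample projections, to be updated as data come in. The footnotes to the Schedule of Assessments follow participants to the endpoint, diabetes or the end of the trial, which is not defined.

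SAP section 7 (Timing of Analyses) gives a third condition: 64 to 70 events in the placebo group.

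**The concern.** An event trigger and a minimum follow-up are both reasonable ways to end a time-to-event trial. Stated together without precedence, they work only if they fall at about the same time. If the events arrive first, the team must choose between analysing at 80 events, when the latest enrolees have less than two years, and waiting, which the trigger wording does not provide for. That choice could then be made with emerging data in view.

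At stake are the secondary comparison of time to Stage 3 and the length of safety observation. If the effect is smaller than assumed, the extra composite events from waiting also matter. The primary test at the design effect is not at stake.

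**Working it through.** **Inputs** (Protocol 8.4, repeated in SAP section 5)
- Placebo: "40% two-year event rate in the placebo group", so the hazard is −ln(0.60)/2 = 0.2554 per year.
- Hydroxychloroquine at hazard ratio (HR) 0.50: 0.1277 per year, i.e. 1 − exp(−0.2554) = 22.5% at two years, as stated.
- 135 and 66 participants at 50 per year: accrual A = 201/50 = 4.02 years, so everyone reaches two years at 6.02 years.
- Dropout below 10% over two years. At the bound, δ = −ln(0.90)/2 = 0.0527 per year.
- Final boundary 1.969 (Protocol 8.5).

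**Step 1: the plan's own figure.** Schoenfeld with 2:1 allocation: (1.960 + 0.954)² / [(2/9)(ln 2)²] = 79.5, so 80 events. Power with the final boundary is Φ(√(80 × 2/9) × 0.693 − 1.969) = Φ(0.954) = 83.0%. Both stated figures reproduce.

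**Step 2: expected events by calendar time T.** For one arm, with uniform accrual and θ = λ + δ:

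E(T) = (n/A)(λ/θ){A − [exp(−θ(T − A)) − exp(−θT)]/θ}

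At T = 6.02 and 10% dropout:
- Placebo: 16.42 × 0.829 × [4.02 − (0.540 − 0.157)/0.308] = 37.8
- Hydroxychloroquine: 33.58 × 0.708 × [4.02 − (0.697 − 0.338)/0.180] = 48.2
- Total: 86.0, above 80

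**Step 3: solve for 80 events at HR 0.50.** The last enrolee's follow-up is the trigger time minus 4.02. The number short of two years is 201 × (6.02 − trigger)/4.02.

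| Two-year dropout | 80th event (years) | Last enrolee (years) | Short of 2 years | Events at 6.02 years |
|---|---|---|---|---|
| 10% | 5.61 | 1.59 | about 21 | 86 |
| 5% | 5.39 | 1.37 | about 31 | 90 |
| 0% | 5.22 | 1.20 | about 40 | 94 |

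In simulation the trigger preceded 6.02 years in about 83% of trials at 10% dropout and about 99% with none.

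**Step 4: sensitivities**
- *Detection delay (an assumption).* A 4-month lag gives 5.94 years at 10% dropout and 5.55 with none. Simulating six-monthly OGTTs plus one month for confirmation gives medians of about 6.0 and 5.5 years. The Figure 3 caption (Protocol 2.1.2) gives 38% for confirmed abnormal glucose tolerance, so adding delay to the 40% may count it twice.
- *Weaker effect* (10% dropout, no lag): 5.05 years at HR 0.65 and 4.34 at HR 1.0. The shares short of two years are (6.02 − 5.05)/4.02 = 24% and (6.02 − 4.34)/4.02 = 42%.
- *Placebo rate 38%:* 5.87 years.
- *Dropout beyond the stated bound:* 6.15 years if 10% is annual and 6.23 at 20% over two years. The minimum is then met.
- *Accrual over 3 years* (67 per year): 79.6 events when the last enrolee reaches two years, so the two conditions coincide. At the planned rate they do not.

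**Step 5: cost if data were cut at the trigger** (10% dropout, no lag)
- HR 0.50: 80 versus 86 composite events. Power at 86 is Φ(√(86 × 2/9) × 0.693 − 1.970) = 86%, against 83%.
- HR 0.65: 80 versus 96 events, power 44% versus 51%.
- Stage 3 at HR 0.50, simulated with the documents' 68% four-year Stage 2 to 3 risk taken as exponential in both arms: about 32 versus 37.

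**Step 6: alpha.** Keeping the interim at 40 events and z = 2.963, the recomputed final boundary is 1.969 at 80 events, 1.970 at 86 and 1.973 at 107.

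**Step 7: the SAP section 7 trigger.** Only 66 participants are planned on placebo and about 38 placebo events are expected at 6.02 years (Step 2). A count of 64 to 70 is not compatible with the 80-event rule.

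**The case against.** The strongest reply is that the text can be read without conflict. Protocol 8.4 places the test after two years on all participants and also speaks of a final test up to the six-year point, so both conditions may be meant to apply. This reading is available, and it is the rule recommended below. But the trigger sentences are unconditional, so the text does not establish it.

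A second reply is that the timeline is a projection, with study-end updates going to the DSMB and the TrialNet governing body and amendment possible. That gives a route for dealing with early events, but not a rule. What is named as a projection is the accrual period and the sample, not the two-year minimum.

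A third is that the gap is small. At 10% dropout with a 4-month lag it is about a month at most, for about 2% of participants, and simulated visit delay closes it. This stands for that corner of the assumptions. It does not hold at lower dropout, which the plan's bound allows, or at weaker effects.

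A reader might also infer that late enrolees will be cut short and diabetes events lost. The documents do not support this. No passage ends follow-up at the 80th event, and Protocol 3.9.2 lets Stage 2 participants stay until Stage 3 or entry into another trial. Nor is the primary analysis underpowered, since 80 events give the planned 83%.

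**Conclusion.** The point holds as an unresolved precedence between two stated conditions. Under the plan's inputs the 80th event is expected 0.4 to 0.8 years before everyone has two years of follow-up. With added detection delay the gap runs from about half a year to nothing. It widens as the effect weakens.

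The consequence is conditional on data being cut at the trigger, and is modest at HR 0.50 and 10% dropout. The Stage 3 difference of about 5 is an upper bound, because staying after Stage 2 is optional and entry into another trial censors. With no dropout the differences are about 14 composite and 12 Stage 3 events.

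These are expectations that rest on exponential times, uniform accrual at 50 per year and dropout within the stated bound.

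**What to change.** - In Protocol 3.9.1 and 8.4 and SAP section 5, state that the final analysis takes place at the later of 80 confirmed events and 24 months after the last randomisation.
- State that the final critical value is recomputed from the spending function at the actual event count.
- Define the data cut-off and the end of the trial.
- Replace the placebo-group trigger in SAP section 7 with the same rule. Otherwise the SAP still contradicts itself.

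If the sponsor prefers a pure event trigger, delete the two-year minimum and state the last enrolee's expected follow-up (about 1.2 to 2.0 years at HR 0.50).

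The cost is wording in both documents and some calendar time. At 10% dropout and no lag, the final analysis comes 6.02 − 5.61 = 0.41 years (about five months) later at HR 0.50 and 6.02 − 4.34 = 1.7 years later if there is no effect. At the planned accrual rate this stays within the roughly six years already planned. The effect on the critical value is negligible.

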## 8.5. Interim Monitoring Plan

A formal interim analysis of efficacy will be conducted when 50% of events (i.e., information fraction = 0.50) have been observed; i.e., we will conduct an interim analysis to compare the two treatment arms when 40 participants enrolled on this trial have a reported progression to Stage 2 or 3 T1D. To preserve the Type I error rate control for each of these comparisons on superiority, the Lan-DeMets error spending rate function with the O'Brien-Fleming boundaries is utilized. If these boundaries are crossed, then the TrialNet DSMB will determine if accrual to that arm should be suspended and/or if treatment of participants should be modified based on these results. The interim and final analysis boundaries and characteristics were generated using the East 6 clinical trial software program (version 6.3, Cytel Inc).

Information fraction	Cumulative events	Alpha spent	Efficacy boundary (p-value)
0.50	40	0.0031	2.963 (or -2.963)
1.00	80	0.00153	1.969 (or -1.969)

The DSMB may terminate the trial prematurely if a statistically significant effect is observed and it is considered that all major trial objectives have been met.

In lieu of a formal futility rule at the interim analysis (i.e., 50% information), we will utilize conditional probability methods to assess the probability that hydroxychloroquine will delay time to T1D stage progression based on the data observed at that point if the observed hazard ratio is  $>1.05$  (i.e., in favor of placebo).

The DSMB will also consider early termination due to absence of a treatment effect (i.e., futility) based on computations of conditional power conducted both under the initial study design and under the current trend of the data.

## **8.6. Withdrawal Criteria – Individual Participants**

An intention-to-treat approach will be used in these analyses. Participants will not be replaced. All data acquired prior to termination for the reasons outlined below will be included in the primary analysis unless a participant withdraws consent for the use of those data. Every effort will be made to conduct a final study visit with the participant, and participants will be followed clinically until, if applicable, all potentially study-related adverse events resolve.

- Withdrawal of consent by the participant
- Withdrawal of the participant by the investigator
- Intercurrent illness or event that precludes further visits to the study site or ability to evaluate disease.

## **9. ETHICAL CONSIDERATIONS AND COMPLIANCE WITH GOOD CLINICAL PRACTICE**

### **9.1. Statement of Compliance**

This study will be conducted in compliance with the protocol and consistent with current Good Clinical Practices (GCP), adopting the principles of the Declaration of Helsinki, and all applicable regulatory requirements (*ICH E6, 45CFR46, and FDA 21CFR sections 11, 50, 56, 312*).

Prior to study initiation, the protocol and the informed consent documents will be reviewed and approved by a Central Institutional Review Board (CIRB) or an appropriate Independent Ethics Committee/Research Ethics Board (IEC/REB) or Institutional Review Board (IRB). Any amendments to the protocol or consent materials must also be approved before they are implemented.

### **9.2. Participating Centers**

Participating TrialNet clinical sites must have an appropriate assurance, such as a Federal-wide Assurance (FWA) or an Unaffiliated Investigators Agreement (UIA), with the Office for Human Research Protections (OHRP), since they are actively engaged in research and obtain informed consent. The protocol and consent forms will be approved by a Central Institutional Review Board (CIRB) or Institutional Review Boards or Ethics Committees/Research Ethics Boards at each of the participating clinical sites. HIPAA and applicable local regulations will be followed by each participating institution in accordance with that institution's requirements. The participating international sites will obtain

approval from their corresponding review boards in accordance with their local procedures and institutional requirements.

The investigator is required to keep accurate records to ensure the conduct of the study is fully documented. The investigator is required to ensure that all source documents are legibly completed for every participant entered in the trial.

The investigational sites participating in this study will maintain the highest degree of confidentiality permitted for the clinical and research information obtained from participants in this study. When a participant participates in this study at more than one TrialNet site, sharing of this information is required. Sharing of information obtained during this study between the TrialNet Hub, TrialNet Clinical Centers and affiliates will occur whenever necessary to assure participant understanding and consent, safety, and adherence to protocol according to country-specific guidelines.

### **9.3. Informed Consent**

The process of assuring that individuals (and parent/guardian if less than 18 years of age) are making an informed decision about participating in this study includes both verbal and written communication. Written materials include a Volunteer Handbook, Volunteer Understanding Assessment, and written or electronic consent forms. The consent form describes the procedures, risks and benefits for the study. The consent forms will be reviewed with participants (and their parent/guardian in the case of participants under 18 years of age) and the participant will be given time to review the written or electronic consent form and ask questions. An assent form has also been developed for participants less than 18 years of age (unless local IRB/REB requirements differ in procedure).

As part of the informed consent process, prior to treatment, the participant and/or parent or guardian (if the participant is less than 18 years of age) will also be required to complete a short, written Volunteer Understanding Assessment that is designed to ensure that the participant understands the study, as well as what is being asked of him/her. The participant will have access to a copy of their consent/assent forms.

The consent process will be conducted by qualified study personnel (the Trial Investigator or Study Coordinator and/or other designee). All participants (or their legally acceptable representative) must read, sign and date a written form prior to participation in the study, and/or undergoing any study-specific procedures.

Remote informed consent may be used as needed when a participant is unable to travel to a TrialNet site. When providing remote consent (via phone or video conference) the POC will review the checklist and long-form informed consent document with the subject/parent or guardian. After the subject/parent or guardian is provided the printed long form informed consent document, the POC will address any questions the subject/parent or guardian may have before the informed consent form is signed and any procedures are performed. The informed consent document may be provided to the subject/parent or guardian using any method that the complete content can be available in print. Signed and completed documentation must be available to the subject/parent or guardian and the study team, by any method that assures that the complete content can be available in print.

Written assent for participants <18 years old may be waived if enrolled using the remote informed consent process. Written assent will be obtained at the participant's next in-person visit.

When a participant turns 18 they are permitted to re-consent remotely should they be unable to return to the study site for an in-person visit. Re-assent when a participant reaches age 12 is waived until the participant returns for an in-person visit at the study site.

The informed consent form must be updated or revised whenever there is new, clinically significant information applicable to the safety of the participants, when indicated for a protocol amendment, and/or whenever any new information becomes available that may affect a participant's participation in the study.

Participants will be re-consented if they reach the age of 18 years while enrolled in the study.

#### **9.4. Study Participant Confidentiality**

The investigational sites participating in this study will maintain the highest degree of confidentiality possible for the clinical and research information obtained from participants. Participant-identifying clinical and research information will be shared between TrialNet sites to support participants and assure protocol compliance as applicable. As a part of the quality assurance and legal responsibilities of an investigation, the investigational site must permit authorized representatives of the sponsor(s) and regulatory agencies to examine (and when required by applicable law, to copy) records for the purposes of quality assurance reviews, audits, and evaluation of the study safety and progress. Unless required by the laws permitting copying of records, only the coded identity associated with documents or other participant data may be copied (obscuring any personally identifying information). Authorized representatives, as noted above, are bound to maintain the strict confidentiality of medical and research information that may identify individuals. The investigational site will normally be notified in advance of auditing visits. Study records with the study participant's information for internal use at the clinical sites will be secured at the study site during the study. At the end of the study, all records will continue to be kept in a secure location. There are no plans to destroy the records.

Study participant data, which is for reporting purposes, will be stored at the TrialNet Coordinating Center. Case report forms sent to the Coordinating Center will identify participants by their unique TrialNet Identification Number. The data entry system at the Coordinating Center is a secured, password-protected computer system. At the end of the study, all study databases will be archived at the Coordinating Center, and the data collection forms will be electronically scanned and saved in electronic format for long-term storage.

Stored samples including genetic samples could be utilized to learn more about causes of T1D, its complications (such as eye, nerve, and kidney damage) and other conditions for which individuals with diabetes are at increased risk, and how to improve treatment. The results of these future analyses, and any mechanistic studies, will not be made known to the participant.

